Phase Two Randomized Controlled Crossover Trial of Atomoxetine to Treat Memory Impairment due to Multiple Sclerosis

Principal Investigator [name]

Primary Department Neurology

Application Initiated By [name]

Lay Summary

Approximately half of persons with multiple sclerosis (MS) develop memory dysfunction, which makes it difficult to maintain gainful employment, manage a household, and lead a fully-engaged social life. There are currently no validated symptomatic treatments for memory deficits in persons with MS. We will perform a pilot fourteen-week double-blind cross-over phase-two randomized controlled trial (RCT) of atomoxetine (80mg qd) versus placebo to improve memory in MS patients with documented memory impairment. Atomoxetine is a non-stimulant selective norepinephrine reuptake inhibitor FDA-approved to treat cognitive-behavioral symptoms of attention deficit / hyperactivity disorder (ADHD; Strattera, Eli Lilly). Pre-clinical evidence suggests that atomoxetine may also improve memory by targeting brain mechanisms responsible for memory function (norepinephrine in the hippocampus). Twenty-four MS patients demonstrating objective memory impairment on neuropsychological screening tests will be randomly assigned to once-daily orally-administered atomoxetine or identically-encapsulated placebo for the first phase, followed by a two-week washout period, and then six weeks of the cross-over condition. The RCT will be performed at the Corinne Goldsmith Dickinson Center for MS at the Icahn School of Medicine at Mount Sinai. Baseline and follow-up evaluations will assess change on Primary Outcomes (objective memory function on neuropsychological tests and patient-reported memory change) and Secondary Outcomes (additional objective and self-reported memory measures; objective and self-reported cognitive efficiency measures; fatigue and mood). We predict that atomoxetine will lead to significantly greater improvements in Primary and Secondary memory outcomes relative to placebo. Consistent with the ADHD literature, there may be additional effects of atomoxetine versus placebo on Secondary cognitive efficiency outcomes. Results of this trial will inform decisions / planning for a possible phase 3 trial, which may ultimately support the use of non-stimulant, once-daily atomoxetine as a memory treatment option for MS patients.

IF Number IF1930708

3. Summary - Setup

Funding Has Been Requested /

Obtained

Yes

Application Type Request to Rely on Mount Sinai IRB

Research Involves Prospective Study ONLY

Consenting Participants
Requesting Waiver or Alteration
of Informed Consent for Any

Yes No

Procedures

Humanitarian Use Device (HUD)
Used Exclusively in the Course of

No

Medical Practice

Use of an Investigational Device to Evaluate Its Safety or Effectiveness

Banking Specimens for Future

No

Research

No

Cancer Related Research that Requires Approval from the Protocol Review and Monitoring

Committee (PRMC).

Is this Cancer Related Research? Cancer Related Research is defined as research that has cancer endpoints or has a cancer population as part of or all of its targeted population. This includes protocols studying patients with cancer or those at risk for cancer.

Clinical Trial Yes

* A prospective biomedical or behavioral research study of human subjects that is designed to answer specific questions about biomedical or behavioral interventions (drugs, treatments, devices, or new ways of using known drugs, treatments, or devices).

* Used to determine whether new biomedical or behavioral interventions are safe, efficacious, and effective.

Drugs / Biologics

Yes

- * Drugs / Biologics That Are Not a Part of Standard Practice
- * Controlled Substances
- * Drugs / Biologics Supplied by the Research Sponsor or Purchased with Study Funds

Ionizing Radiation for imaging or therapy, including X-Ray, Fluoroscopy, CT, Nuclear Medicine, PET andor Radiation Therapy:

- * Purely for standard of care:
- * In frequency or intensity that exceeds what is necessary for standard of care:

No

Hazardous Materials

No

- * Recombinant DNA
- * Viral Vectors

- * Plasmids
- * Bacterial Artificial Chromosomes
- * Toxic Chemicals, Potentially Toxic Medications, Carcinogens * Autologous Cell Lines

Request Use of Clinical Research Unit Resources No

4. Summary - Background

Objectives

- 1. Investigate whether treatment with atomoxetine (versus placebo) improves (a) memory on objective cognitive tasks and (b) patient-reported memory in MS patients with documented memory impairment.
- 2. Investigate whether atomoxetine (versus placebo) also has beneficial effects on (a) cognitive efficiency on objective cognitive tasks, (b) patient-reported attention/organization, and (c) fatigue and mood.

Background

Memory Impairment in Multiple Sclerosis: Most persons with multiple sclerosis (MS) are diagnosed between ages 20 and 40,[1] while they are striving to finish education, establish careers, and manage households. About half of MS patients will suffer memory decline,[2-4] which begins early in the disease[4,5] and negatively impacts quality of life (e.g., unemployment).[3,6] Despite the high prevalence and debilitating consequences of memory decline in MS patients, there are currently no validated symptomatic memory treatments.[7-9] We have reported preliminary support for levo-amphetamine (I-AMP) as an effective memory treatment in MS, with memory-impaired patients showing a 50% improvement on objective memory tasks relative to placebo,[10] with no effects on processing speed.[11] It is instructive that I-AMP, classified as a stimulant, improved memory rather than speed. Although both stimulants, I-AMP and dextro-amphetamine (d-AMP, prescribed for ADHD) have different mechanisms of action: d-AMP works on dopaminergic targets in the frontal lobe (e.g., striatum) to increase attention, whereas I-AMP targets norepinephrine pathways, with a greater impact on hippocampal structure and memory in rodents.[12] Unfortunately, I-AMP is not FDA-approved for any indication, and there is no industry support to perform the necessary phase 3 trials required for FDA approval. As such, I-AMP is not a viable option for treatment of MS memory impairment; however, the aforementioned preliminary data on I-AMP and memory provide critical guidance toward an even more promising non-stimulant option: atomoxetine.

Atomoxetine and Memory: Atomoxetine (Strattera, Eli Lilly) is a non-stimulant selective norepinephrine reuptake inhibitor FDA-approved for treatment of ADHD.[13] Neuropharmacologically, atomoxetine leads to increased norepinephrine in the cortex and hippocampus, without increases in dopamine within the striatum or nucleus accumbens,[14,15] which explains reduced risk of locomotor activation and addiction / abuse when using atomoxetine versus stimulant medication (e.g., methylphenidate, for review[16]). Clinical trials in ADHD have understandably focused on outcomes of inattention and hyperactivity; however, positive effects of atomoxetine on visual memory have also been reported,[17] consistent with (a) positive effects on memory in rodents,[18] (b) the importance of norepinephrine for memory generally,[19] and (c) human cerebral blood flow evidence showing that atomoxetine differentially increases mesial temporal blood flow relative to placebo and methylphenidate.[20]

Atomoxetine as a Memory Treatment in MS: MS patients experience hippocampal atrophy beginning early in the disease, [21-23] histological studies document substantial hippocampal demyelination and synaptic loss, [24-26] and work from our group and others has linked MS memory deficits with hippocampal structure and function (e.g., [21,27-30]). Consistent with aforementioned roles of atomoxetine on hippocampal norepinephrine and memory, and preliminary effects of I-AMP on memory in MS[10] (likely via norepinephrine[12]), there is adequate evidence to support a pilot clinical trial of norepinephrine reuptake inhibition with atomoxetine as a potential symptomatic treatment of memory impairment in MS. An important practical consideration supporting this proposal is that atomoxetine is already FDA-approved, so the path to clinical use for memory impairment in MS patients is more straightforward. Finally, there are important physiological, psychological, and regulatory barriers to stimulant medication use, which are circumvented by use of the non-stimulant atomoxetine.

References:

- 3. At the same three time points, we will measure performance on four cognitive efficiency tasks assessing processing speed (Symbol Digit Modalities Test, Oral Version: Total Correct), sustained attention/continuous performance (CANTAB Rapid Visual Information Processing: RVP A'), reading comprehension speed (Woodcock Johnson Reading Fluency), and working memory (WAIS-IV Digit Span: total raw score).
- 4. Patient Reported Outcomes of (a) cognitive efficiency assessed with Attention and Planning/Organization subscales of the PDQ; (b) fatigue assessed with the Fatigue Severity Scale; (c) mood assessed with the Beck Depression Inventory Fast Screen, and (d) suicidal ideation with the Columbia Suicide Severity Rating Scale.

Protocol Was Already Approved
by the Icahn School of Medicine at
Mount Sinai (ISMMS) Institutional
Review Board (IRB) Under a
Different Principal Investigator

Protocol Was Previously Submitted No to an External(non-ISMMS) IRB

5. Research Personnel

Name/Department	Role/Status	Contact	Access	Signature Authority	Phone	Email
[name] / Neurology	Principal Investigator /		Signature Authority			
[name] /	ARC /		Edit Access			
[name] /	CI /		Edit Access			
[name] /	ARC /		Edit Access			

6. Sites

Site Name Icahn School of Medicine at Mount Sinai

Other External Site Name

Contact Details

Approved

Approval Document

Funded By Mount Sinai

Other IRB

7. Subjects - Enrollment

Site Name Icahn School of Medicine at Mount Sinai

Subjects To Be Enrolled

30

Total Number of Subjects to be Enrolled Across All Listed Sites Above (Auto Populated) 30

Page 10 of 32

8. Subjects - Populations

Inclusion Criteria

- 1. Diagnosis of Multiple Sclerosis based on the Revised McDonald criteria (Polman. Ann Neurol 2011; 69: 292-302)
- 2. Age 21 60 years.
- 3. Memory Impairment on validated neuropsychological memory screening tests, as follows:
- a) performance #16th percentile on both Rey Auditory Verbal Learning Test (RAVLT) Total Learning and WMS-IV Visual Reproduction (Immediate); and
- b) mean normative performance is at least 1.0 standard deviation below expectations based on premorbid IQ (WTAR provides estimates of expected memory function).
- 4. Patient self-report of memory decline from previously higher level of functioning.

Exclusion Criteria

- 1. Current stimulant medication usage.
- 2. Previous diagnosis or treatment for ADHD or any neurologic condition other than multiple sclerosis (e.g., traumatic brain injury, epilepsy)
- 3. clinical relapse of MS within 60 days of screening,
- 4. change in disease-modifying therapy within 90 days of screening,
- 5. below average estimated premorbid intelligence (WTAR score #16th percentile),
- 6. severe cognitive impairment indicated by a Mini Mental Status Examination (MMSE) < 24/30,
- 7. contraindications for atomoxetine use: (a) self-reported history of suicidal ideation within the last twelve months (Columbia Suicide Severity Rating Scale), (b) diagnosis of bipolar illness, (c) moderate or severe current depressive symptomatology (Beck Depression Inventory Fast Screen # 9), (d) diagnosis of hepatic disease, (e) narrow angle glaucoma, (f) pheochromocytoma, (g) monoamine oxidase inhibitor within 14 days of study drug start, (h) taking strong CYP2D6 inhibitors (e.g., paroxetine, fluoxetine, quinidine), (i) diagnosis of heart disease, (j) pregnant or planning pregnancy during the study period, (k) breastfeeding, (l) hypersensitivity to atomoxetine or component of formulation. Note that in the case where a potential subject is receiving medication for care that interacts with atomoxetine, her / his clinical regiment will not change to allow for study entry.

Enrollment Restrictions Based Yes
Upon Gender, Pregnancy,
Childbearing Potential, or Race

Justify Restriction(s)

We are excluded women who are pregnant or planning to become pregnant during the study period. Pregnancy risk associated with atomoxetine is category C (risk cannot be ruled out).

Age Range(s) 18 to 64 Years
Targeted Population(s) Adults - Patients

Other Aspects that Could Increase Subjects Vulnerability

None.

Safeguards to protect Subjects rights and welfare

We are employing inclusion / exclusion criteria which minimize risk to patients from atomoxetine, and we will monitor side effects. We will also emphasize the voluntary nature of this study, and that there is no penalty for withdrawal.

9. Subjects - Participation

Duration of an Individual Subjects Participation in the Study

Once consented and screened, the baseline will be completed and the rest of the study will take fourteen weeks: sixweek phase one, two-week washout, six-week phase two.

Duration Anticipated to Enroll All Study Subjects

One year

Estimated Date for the Investigators Within one year to Complete This Study

Procedures for Subjects to Request Withdrawal

Subjects who desire to discontinue participation in this study will contact the study coordinator via telephone or email to withdraw.

The information collected prior to subject withdrawal may be used if deemed necessary to complete the study. As an FDA regulated study, the data cannot be destroyed. Data will not be distributed to anyone.

Procedures for Investigator to Withdraw Subjects

The investigator will withdraw subjects who fail to complete the baseline or follow-up evaluation, or who report serious side effects of the study medication as determined by Co-I [name] [name]. (attending MS neurologist).

The information collected prior to subject withdrawal may be used if deemed necessary to complete the study, unless the subject informs us in writing that they withdraw the data collected and the samples collected. Previously collected data can only be withdrawn if it has not yet been de-identified and distributed.

Participants Will Be Recruited Yes

Recruitment Method(s) Clinical Practice

How Participants Will Be Identified

Patients meeting inclusion criteria for age and MS diagnosis will be as asked by their treating physician, nurse practitioner, or neuropsychologist if they would be interested in hearing more about the study. If the patient is interested in participating and reports subjective difficulty with memory, a member of the research team will either speak with them in person, or they will be asked if they want to be contacted by a member of the research team at another time, or they will be given contact information for a member of the research team. If the patient is interested and would prefer to be contacted, the clinician will provide us with the name and best way to contact them. We also have a list of patients who have asked us to contact them if we have any enrolling research studies. We will contact those patients at their preferred contact.

Who Will Initially Approach Member of Primary Care Team, Treating

Potential Participants Physician
How Research Will Be Introduced to Participants

Patients will be asked by their physician, nurse practitioner, or neuropsychologist if they are interested in learning about a placebo-controlled RCT of a drug aiming to improve disease-related memory decline. Patients will be told that atomoxetine is a non-stimulant drug FDA-approved to treat ADHD, but that the use of atomoxetine to treat memory deficits is not an approved use of the drug. Patients will be told that it is a cross-over design, and that they will receive atomoxetine during one phase, and placebo during the other, but that he/she will not be blinded to phase. If they are interested, patients will be referred to the study personnel as noted above.

How Participants Will Be Screened

Inclusion and exclusion criteria will be reviewed with patients via telephone or in-person screening with study personnel. Patients who report memory difficulties and meet demographic eligibility criteria will be invited to the MS Center for a brief twenty-minute in-person screening. After informed consent, the screening will include two memory screening tests (RAVLT, WMS-IV Visual Reproduction), a word-reading estimate of premorbid IQ (WTAR), a depression screening tool (BDI-FS), and an assessment of suicidal ideation with the past six months (Columbia Suicide Severity Rating Scale). Demographic (e.g., age) and medical (e.g., last relapse) will be reviewed with the patient and/or their medical record. All current medications will be recorded, and Co-I [name] [name]. will review for possible interactions with atomoxetine.

10. Procedures - Narrative

Description of the Study Design

This is a double-blind randomized placebo-controlled cross-over design whereby each of 24 enrolled MS patients (meeting inclusion criteria / screening) will complete the following:

- 1. Baseline Evaluation (neuropsychological, psychological, self-report, and motor assessment; about 1 hour).
- 2. Phase One Drug: Six weeks of treatment with atomoxetine or placebo (randomly assigned)
- 3. Phase One Evaluation: baseline evaluation repeated on the last day of phase one.
- 4. Two week washout period
- 5. Phase Two Drug: Six weeks of opposite condition as phase one (i.e., if atomoxetine in phase one, then placebo in phase two)
- 6. Phase Two Evaluation: baseline evaluation repeated on the last day of phase one.

Description of Procedures Being Performed

After informed consent, subjects will engage in a 30-minute screening consisting of memory tests (Rey Auditory Verbal Learning Test, Visual Reproduction of the Wechsler Memory Scale, Fourth Edition), word-reading test (Weschler Test of Adult Reading), depressive symptoms (Beck Depression Inventory, Fast Screen), and assessment of suicidal ideation within the past twelve months (Columbia Suicide Severity Rating Scale).

Patients who meet all inclusion criteria will advance to the fourteen week crossover trial.

- 1. Baseline Evaluation:
- a. Memory Tests: Selective Reminding Test, Brief Visuospatial Memory Test, Revised, CANTAB Paired Associate Learning, NIH Toolbox Picture Sequence Memory Test (PSMT)
- b. Cognitive Efficiency Tests: Symbol Digit Modalities Test, CANTAB Rapid Visual Information Processing, Woodcock Johnson Reading Fluency, WAIS-IV Digit Span
- c. Questionnaires: Perceived Deficits Questionnaire (self-report of cognitive/memory deficits), Beck Depression Inventory, Fast Screen (mood), Fatigue Severity Scale (fatigue), Columbia Suicide Severity Rating Scale (suicidal ideation)
- d. Motor Tasks: 25-foot walk, Nine Hole Peg Test

2. Phase One Drug:

Patients will receive atomoxetine or identically encapsulated placebo from the research pharmacy. They will receive two containers: one containing seven 40mg capsules, and one containing enough 80mg capsules for the remaining five weeks. Subjects will be instructed to take the 40mg dose once per day (in the morning) for the first seven days, and then switch to the 80mg dose once per day (in the morning) for the remainder of Phase One. Subjects will be encouraged to set an alert in their smartphones to remind them to take the capsule at the same time each day. Subjects will also be provided with information about atomoxetine (Strattera) provided by the pharmaceutical company (Eli Lilly). Patients will be instructed not to take more than one capsule per day. If they miss a dose, they should keep it in the container. All remaining capsules will be returned to the investigator at the end of the six weeks (when the subject returns for the first follow-up). Patients will also be instructed to contact the study team immediately if they experience any side effects.

3. Phase One Evaluation: The baseline evaluation will be repeated on the last day of Phase One. Alternate forms will be used as appropriate. In addition, patients will be asked to guess which type of capsule they were tasking, and also complete an additional questionnaire:

Patient-Reported Memory Change: Patients will endorse global memory change over the past month as: much improved (3), somewhat improved (2), mildly improved (1), unchanged (0), mildly worse (-1), somewhat worse (-2), much worse (-3).

4. Two week washout period.

Patients will go two weeks without taking any study capsule.

5. Phase Two Drug

The same procedures as Phase One will be followed, except that patients will receive the opposite capsules as Phase One.

6. Phase Two Evaluation

The same procedures as the Phase One Evaluation will be repeated.

Description of the Source Records that Will Be Used to Collect Data About Subjects

Paper source records will include demographic information, general medical history, and MS medical history information; however, there will be no PHI on any source forms. All data will be collected using paper neuropsychological record forms and/or score sheets. CANTAB tasks are performed on an iPad; however, no PHI will be entered into the iPad. Instead, CANTAB scores will be transferred to paper score sheets. All data will be entered into a RedCap database, which will include no PHI.

Description of Data that Will Be Collected Including Long-Term Follow-Up

This is documented above.

Research Requires HIV Testing

Page 15 of 32

11. Procedures - Genetic Testing

Genetic Testing Will Be Performed No
Guidance and Policies > Future Use Data Sharing and Genetic Research

Page 16 of 32

12. Procedures - Details

Surveys or Interviews Yes

Type of Instruments Being Used Standardized, Created By Research Team

Names of Standardized Instruments

NEUROPSYCHOLOGICAL INSTRUMENTS

Rey Auditory Verbal Learning Test

Visual Reproduction of the Wechsler Memory Scale

Brief Visuospatial Memory Test, Revised

Selective Reminding Test

CANTAB Paired Associate Learning

NIH Toolbox Picture Sequence Memory Test

Symbol Digit Modalities Test

CANTAB Rapid Visual Information Processing

Woodcock Johnson IV Reading Fluency

Wechsler Adult Intelligence Test, Third Edition: Digit Span

Wechsler Adult Reading Test

25-Foot Walk

Nine Hole Peg Test

QUESTIONNAIRES

Perceived Deficits Questionnaire

Beck Depression Inventory, Fast Screen

Fatique Severity Scale

Columbia Suicide Severity Rating Scale

Description of Instruments Created By Research Team

Patient-Reported Memory Change: Patients will endorse global memory change over the past month as: much improved (3), improved (2), slightly improved (1), unchanged (0), slightly worse (-1), worse (-2), much worse (-3).

Audio / Photo / Video Recording	No
Deception	No

Results of the Study Will Be Shared No with Subjects or Others

13. Procedures - Instruments

Instruments Created By Research Team

Type Questionnaire

NamePatient Reported Memory ChangeUploadMEMORY QUESTIONNAIRE.docx

Type Questionnaire (Revised)

Name Patient Reported Memory Change
Upload Memory Questionnaire Revised.docx

Page 18 of 32

14. Procedures - Compensation

Compensation for ParticipationYesTypeCheckAmount Per Visit10# of Visits1Line Total10JustificationTime

Who Will Pay

Specify Who Will Pay

Comment

For completion of baseline evaluation

Type Check
Amount Per Visit 20
of Visits 1
Line Total 20
Justification Time

Who Will Pay

Specify Who Will Pay

Comment

For completion of Phase One Follow-up

Type Check
Amount Per Visit 20
of Visits 1
Line Total 20
Justification Time

Who Will Pay

Specify Who Will Pay

Comment

For completion of Phase Two Follow-up **Total Compensation**50

PI must attest that all of the following are true.

- * Credit for payment accrues as the study progresses.
- * Payment is not contingent upon completing the entire study.
- * The amount of payment and the proposed method and timing of disbursement is neither coercive nor presented undue influence.
- * Any amount paid as a bonus for completion is reasonable and not so large as to unduly induce subjects to stay in the study when they would otherwise have withdrawn.
- * All information concerning payment, including the amount and schedule of payments, is in the informed consent document.
- * Compensation does not include a coupon good for a discount on the purchase price of the product once it has been approved.

15. Consent - Obtaining Consent

Consent Process Adult Consent

Where and When Consent Will Be Obtained

Consent will be obtained in the Corinne Goldsmith Dickinson Center for MS (MS Center) at Mount Sinai (FPA)

Waiting Period for Obtaining Consent

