Data will be stored in a locked filing cabinet located in a locked closet, within a locked office (PI: [name]). Each lock has a separate key. Only two persons have the key to the filing cabinet: [name] (PI) and the study research coordinators. Data files will be kept separate from identifiable data (PHI), with the exception of a password protected and encrypted Excel file linking subject names and subject numbers. This file will be located on a ISMMS network drive and only accessed from ISMMS computers. Only [name] and the coordinators will have the password. Raw data files may be retrieved by [name] or the research coordinator, and viewed on site in a private office space. Files will not be removed from Mount Sinai Hospital. Files will be immediately returned to their secure location within the filing cabinet.

Power Analysis/Data Analysis Plan (Including Any Statistical Procedures)

[name] will lead statistical analyses, which will consist of dependent T-tests comparing differences in outcomes (e.g., memory composite score) between the drug and placebo phases of the cross-over trial.

20. Data - Safety Monitoring

More Than the Minimum Data Yes Safety Monitoring Will Be Done

Principal Monitor [name]

Additional Monitors

Specific Items That Will Be Monitored for Safety

Suicidal ideation will be monitored with the Columbia Suicide Severity Rating Scale. Subjects who report suicidal ideation at any point in the study will be escorted to the psychiatric emergency department at Mount Sinai Hospital for further evaluation.

Suicidal ideation and other adverse events reported by patients will be recorded. Co-I [name] [name]. will review all adverse events as they are reported, and judge severity. [name] is not involved in data collection or processing, so she can be unblinded to identify whether adverse events occurred during atomoxetine or placebo.

Frequency of Data Review

Suicidal ideation will be evaluated at baseline, first follow-up, and second follow-up for all subjects, and immediate action will be taken if suicidal ideation is present (as noted above).

[name] will also be told immediately of any other serious adverse events, such as allergy to atomoxetine. She will have access to condition assignments in the case of adverse events.

Rules for Alteration of Study Design

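### The screening description in Section 9 gives the C-SSRS a six-month look-back for suicidal ideation, but exclusion 7(a) and the Section 10 screening procedure use twelve months

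*Combined protocol and SAP*

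**What the plan says.** Three places in the combined protocol and SAP give a look-back period for suicidal ideation on the C-SSRS.

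- Section 8, Exclusion Criteria, item 7(a), listed among the contraindications for the study drug: "self-reported history of suicidal ideation within the last twelve months (Columbia Suicide Severity Rating Scale").
- Section 9, How Participants Will Be Screened: "an assessment of suicidal ideation with the past six months (Columbia Suicide Severity Rating Scale").
- Section 10, Description of Procedures Being Performed, screening paragraph: "assessment of suicidal ideation within the past twelve months (Columbia Suicide Severity Rating Scale").

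The Section 9 text opens with a general step: "Inclusion and exclusion criteria will be reviewed with patients via telephone or in-person screening with study personnel".

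Section 20, under safety endpoints, makes suicidal ideation the primary safety outcome. Section 8, under safeguards, relies on the inclusion and exclusion criteria to keep the risk from atomoxetine low.

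**The concern.** Exclusion 7(a) names the C-SSRS as its instrument, so the period over which the C-SSRS is asked at screening bears directly on whether the criterion is applied in full. Section 9 is the part of the protocol headed as the account of how participants are screened, and staff could reasonably work from it. If they do, the instrument is asked over a shorter period than the exclusion covers.

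The stake is that a patient with ideation 6 to 12 months earlier, whom the protocol means to keep out on safety grounds, might not be identified by the named instrument. The matter is confined to eligibility screening.

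**Working it through.** No figure in the plan depends on this point, so the check is a comparison of text.

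**Step 1. Every mention of the C-SSRS by name.**

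| Place | What the text does | Look-back |
|---|---|---|
| Section 8, exclusion 7(a) | decides who is excluded | 12 months |
| Section 9, How Participants Will Be Screened | describes post-consent screening | 6 months |
| Section 10, screening paragraph | describes post-consent screening | 12 months |
| Section 4, secondary endpoint 4(d) | lists the outcome: "suicidal ideation with the Columbia Suicide Severity Rating Scale" | none |
| Section 10, baseline questionnaires | lists the battery: "Columbia Suicide Severity Rating Scale (suicidal ideation") | none |
| Section 12, standardized instruments | lists the instrument | none |
| Section 20, items monitored for safety | "Suicidal ideation will be monitored with the Columbia Suicide Severity Rating Scale" | none |

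That makes 7 mentions: 2 with twelve months, 1 with six months and 4 with no window (2 + 1 + 4 = 7). None of the four silent mentions settles the matter.

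**Step 2. Do Sections 9 and 10 describe the same assessment?** Both place the screening after informed consent, and both list the same five instruments: RAVLT, WMS-IV Visual Reproduction, WTAR, BDI-FS and C-SSRS. They give different durations (twenty minutes in Section 9, 30 minutes in Section 10), but nothing suggests two separate screening sessions. The two windows therefore belong to one step.

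**Step 3. Could the difference come from the PDF extraction or from superseded text?** Both windows are written out in words, so a lost symbol or broken table does not explain it. Neither stands in an amendment log or summary of changes.

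**Step 4. Consequences by time since last ideation, *t* months before screening.**

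| *t* | Exclusion 7(a) | C-SSRS as in Section 10 | C-SSRS as in Section 9 |
|---|---|---|---|
| up to 6 | excluded | asked | asked |
| more than 6, up to 12 | excluded | asked | not asked |
| more than 12 | not excluded | not asked | not asked |

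The conflict lies wholly in the middle row. It spans 12 − 6 = 6 months, or 6/12 = one half of the exclusion window. A patient whose last ideation was nine months before screening falls in it.

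**Step 5. Number of patients.** The documents give no figure for how often ideation was last present in that interval, so no count can be derived.

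**The case against.** The strongest reply is that the protocol has one exclusion rule and that the rule is clear. Only 7(a) decides who is excluded; Sections 9 and 10 describe assessments. The Section 9 text begins by reviewing all criteria with the patient. Because 7(a) is a matter of self-reported history, that review should itself raise the full twelve months. The list of screening tests in Section 9 does not forbid further questions, and Section 10 already has the twelve-month window.

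Much of this stands. A reader might infer that the protocol contains two competing exclusion criteria, one of six and one of twelve months. It does not: no text excludes on a six-month basis, and Section 10 by itself excludes nobody on this ground. A reader might also infer that ineligible patients will be enrolled. The documents do not support that either. It would require staff to follow the Section 9 wording and the criteria review to fail to bring the earlier ideation out.

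The reply does not remove the mismatch. The general review names neither ideation nor a period, whereas the C-SSRS is the instrument that 7(a) names. The repeat C-SSRS at baseline cannot be counted on to fill the gap, since no look-back is stated for it.

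**Conclusion.** The inconsistency is real. One of the three stated look-backs is half the length of the other two, and it stands in screening text for a safety exclusion. It affects patients whose last ideation was more than 6 and up to 12 months before screening, and only to the extent that staff use the Section 9 wording and the criteria review does not make up for it.

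The conclusion rests on one reading, that Sections 9 and 10 describe the same post-consent screening. The shared list of five instruments supports it.

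Because suicidal ideation is also the primary safety outcome, a reader might infer that the safety results are compromised. The documents do not support that: the look-back at screening governs entry only, and no effect on endpoints, analysis or sample size follows. This is a minor correction, worth making because it concerns safety eligibility.

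**What to change.** Reconcile exclusion 7(a) in Section 8, How Participants Will Be Screened in Section 9 and the screening paragraph in Section 10, so that the C-SSRS window asked at screening is the same as the window in the exclusion criterion. Which window is right is for the investigators to settle; this review does not choose one.

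The cost is a few words in the affected text. The design, visits and analysis do not change.
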